Evaluating a Digital Peer Mentoring Platform With College Student Populations

NCT05764785

August 2, 2023

Investigator Protocol

Study Title

Evaluating the acceptability, feasibility, and efficacy of a digital peer mentoring platform with college student populations

Objectives

- **Purpose:** The purpose of the study is to assess the acceptability, feasibility, and efficacy of the MentorPRO application with three University of Massachusetts (UMB) student support program-Directions for Student Potential (DSP).
 - Main outcomes will include attitudes towards the MentorPRO platform, emotional wellbeing (e.g., anxiety, depression), engagement with a third party mental health app, and academic factors (e.g., academic motivation, academic efficacy)
 - **Research Question 1:** What is the acceptability and feasibility of the MentorPRO mentoring platform?
 - **Research Question 2:** Does mentoring with MentorPRO demonstrate an impact on academic outcomes (i.e., GPA), engagement with a mental health mobile application, and indices of wellbeing (i.e., mental health, connectedness, academic self-efficacy, and overall wellbeing) among a diverse sample of incoming or first year college students?
- **Study design:** Every student in the DSP program this summer (and meets the study eligibility criteria) will be eligible to participate in the study. Students who opt into participation in research activities will complete 2 brief surveys.
- **Study intervention:** MentorPRO is a novel application and web platform for mentoring programs that allows students to set goals, track their challenges, and find just-in time resources, while connecting to a mentor for personalized support and progress monitoring. All students in DSP will be matched with a peer mentor. Students will be assigned to getting MentorPRO (intervention condition) or mentoring as usual (control condition), depending on what DSP cohort they are in (a.m. or p.m. classes).
- **Study endpoints (clinical trials):** All students involved in the DSP summer program will be involved in 6 weeks of academic programming and peer mentoring (June 12th-July 21st), meeting 4 days per week during the summer prior to mentees' first year in college, as well as 3 weeks of post-program peer mentoring (total trial of 9 weeks).

Background

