 - All interested participants will read and sign an informed consent, after having time to ask questions to program staff and the research team. Then, they will complete an eligibility screener, and if eligible will complete the rest of the baseline survey.
 - Interested participants will then be prompted to take the first survey after consenting to the study (T1). Students will complete the DSP course for 6 weeks, and will receive peer mentoring during that time. For 3 weeks after the course, students will be able to contact their peer mentor with questions. At the end of the 9-week trial, students will receive a final survey (T2). The eligibility screener, informed consent, and the surveys will be administered via a Qualtrics link. At the conclusion of their participation, all participants will receive a debriefing statement explaining the study and where to find additional resources if needed.
 - Students will be assigned to the intervention or control condition based on what DSP cohort they are part of (a.m. or p.m. classes - the a.m. cohort will be assigned to the intervention/MentorPRO condition, while the p.m. cohort receives mentoring as usual).
 - Mentors will be matched with students who are assigned to both conditions, and therefore all mentors will receive all training materials. In addition to the training in program policies and relationship building provided to program peer mentors, all mentors will undergo training designed by the research team. Mentors will complete a brief orientation to the MentorPROUMB technology, followed by a 30-min interactive online course on providing supportive accountability, through MentorPRO UMB Academy which includes “knowledge checks” to ensure mentors are engaged and understanding the material and tracks progress to ensure course completion. Finally, mentees will be given access to an online orientation to MentorPRO UMB, which walks them

Investigator Protocol

through instructions about how to download and use the app. All study participants (mentors and student mentees) will have access to tech support within 24 hours from Academic Web Pages for any questions or issues that arise.

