STATISTICAL ANALYSIS PLAN

Evaluating a Digital Peer Mentoring Platform With College Student Populations

NCT05764785

August 2, 2023

This study was designed to examine whether using MentorPRO with a peer mentor – compared to peer mentoring-as-usual (control) - during a summer bridge program was related to significantly greater reduction in mental health symptoms and improvement in wellbeing indices. Inclusion criteria included elevated mental health symptoms, 18-years-old or older, English proficiency, and participating in the summer bridge program at University of Massachusetts Boston.

Data Analysis Plan from IRB Protocol:

- **Data analysis:** The data will be analyzed both quantitatively and qualitatively. The procedures are outlined below to address each of the research questions:
 - Research Question 1: What is the acceptability and feasibility of the MentorPRO mentoring program?
 - Recruitment, retention, and adherence to the MentorPRO mentoring program and application will be evaluated to determine the acceptability and feasibility of the program.
 - Acceptability of MentorPRO will also be assessed through open-ended questions and surveys commonly used to evaluate online programs.
 - Qualitative analyses will be conducted to evaluate the level of participants' engagement with mentors via the in-app chat messaging feature.
 - Mentors' responses to survey questions will examine initial mentor feasibility and acceptability of MentorPRO.
 - Research Question 2: Does mentoring with MentorPRO demonstrate an impact on efficacy for student academic outcomes (i.e., GPA) and indices of wellbeing (i.e., mental health, connectedness, academic self-efficacy, and overall well-being) among a diverse sample of incoming or first year college students?
 - Quantitative analyses will be conducted to determine whether level of engagement with mentors and the app (e.g., via frequency of in-app chat messaging, frequency of in-app survey completion and check-ins) relates to changes in academic outcomes and indices of wellbeing, as well as to broadly model how these domains change over the course of students' participation.
 - Group comparisons will be conducted to examine if there are differences in final mental health and wellbeing measures across groups (intervention and control). Baseline demographics and wellbeing indices will be used as covariates in analyses.

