 - Exploratory analyses will also be conducted on the data to examine whether other trends or patterns emerge from the data.
- **Data integrity:**
 - In order to ensure quality control of the data collected via the Qualtrics survey, participants will be prevented from submitting multiple responses by enabling this feature within Qualtrics. Data will be checked for missingness.

The final Clinical Trials report findings will follow this analytic plan. We will report descriptive statistics for the sample and primary and secondary outcome measures. Power analysis will be performed to determine that the sample size is adequate to detect a statistically significant difference given the anticipated effect size. Using intention-to-treat analyses, we will conduct repeated measures ANOVAs with two time points (pre and post summer bridge program), to examine whether significant interactions emerge between time and assigned condition (MentorPRO vs. control) on main outcome measures (depression [PHQ-9] and anxiety [GAD-7])

self-reported symptoms and overall wellbeing) and secondary outcome measures (academic self-efficacy, sense of belonging to the university, and cognitive load). To correct for multiple comparisons, we will use a Bonferroni correction, $\alpha = .05$ divided by six tests, resulting in a final α of .008.

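### With one class cohort per arm, the planned ANOVAs cannot separate MentorPRO from any other a.m./p.m. difference in change, and .008 holds only if there is no cohort-level variance in change

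*Protocol*

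**What the plan says.** **Allocation.** The design bullet under Objectives in the protocol places students in MentorPRO or mentoring as usual "depending on what DSP cohort they are in (a.m. or p.m. classes"). Procedures Involved (student mentees) repeats the rule, "Students will be assigned to the intervention or control condition based on what DSP cohort they are part of", and fixes the direction: "the a.m. cohort will be assigned to the intervention/MentorPRO condition, while the p.m. cohort receives mentoring as usual". Neither document mentions randomisation, or says how students come to be in one cohort or the other.

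**Efficacy test.** In its closing paragraph the SAP says "we will conduct repeated measures ANOVAs with two time points (pre and post summer bridge program"), and that the aim is "to examine whether significant interactions emerge between time and assigned condition (MentorPRO vs. control"). Six outcomes are tested, with .05 "divided by six tests, resulting in a final α of .008".

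**Second comparison.** The Data Analysis section of the protocol, repeated in the SAP, also compares final mental health and wellbeing scores between the groups. On adjustment it says: "Baseline demographics and wellbeing indices will be used as covariates in analyses".

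**What is absent.** Neither document contains a cohort or class term, an ICC, a design effect, or a limit on what may be concluded from the a.m./p.m. contrast. Research Question 2 is worded in terms of impact.

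**The concern.** An ANOVA on individual students measures chance by the spread among students within a cohort. Anything that moves a whole cohort's scores between the two surveys is missing from that error term and goes entirely into the condition contrast. The programme meets four days a week for six weeks, so some change shared among classmates is plausible.

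Two things are at stake. First, a significant interaction would naturally be read as an effect of MentorPRO, although the data cannot tell that apart from another a.m./p.m. difference in change. Second, the Bonferroni threshold suggests a level of error control that the test does not provide for that conclusion. All six efficacy tests are affected, and the second problem grows as more students take part.

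**Working it through.** **1. The plan's own figure.** .05 / 6 = .00833, which rounds to the stated .008. If students were independent, the Bonferroni bound over six tests would be 6 × .008 = .048. The threshold is correctly computed; the question is whether each test runs at that level.

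**2. What the test is.** With two time points, the time-by-condition F test is the same as a two-sample t-test on change scores, with 2m − 2 degrees of freedom for m students per arm.

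**3. Inputs.**
- Cohorts per arm: 1 (protocol, Objectives and Procedures Involved).
- m = 25: inferred from the 1/25 raffle odds under Payment/incentives. It is not a stated sample size.
- m = 150: the capacity of 300 (Number of Participants) split equally. The equal split is an assumption.
- m = 75: half of that ceiling, as an intermediate case.
- ICC of the change score, ρ: .01, .02 and .05. These are assumptions; the documents give no value.

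**4. Formula.** With total change variance set to 1, the test treats the variance of an arm mean as (1 − ρ)/m. The actual variance is ρ + (1 − ρ)/m. The ratio is

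V = [mρ + (1 − ρ)] / (1 − ρ)

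and the actual two-sided error is 2 × P(t > t_crit / √V), where t_crit is the two-sided .008 critical value.

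Worked case, m = 25 and ρ = .02: V = (0.50 + 0.98)/0.98 = 1.510 and √V = 1.229. With 48 df, t_crit = 2.768, and 2.768/1.229 = 2.252. The two-sided tail is .029.

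| m per arm | ρ = .01 | ρ = .02 | ρ = .05 |
|---|---|---|---|
| 25 | .017 | .029 | .075 |
| 75 | .044 | .093 | .229 |
| 150 (ceiling) | .093 | .186 | .371 |

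At ρ = 0 every entry is .008. Simulation with 10,000 replicates agrees: at m = 75 it gave .094 for ρ = .02 and .230 for ρ = .05.

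**5. The same point as a fixed difference.** Suppose MentorPRO does nothing, but the cohorts differ by 0.3 SD in mean change for another reason. The test is then significant with probability .06, .21 and .48 at m = 25, 75 and 150.

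**6. Stable gaps.** A constant 0.5 SD a.m./p.m. gap, present at both surveys, cancels in the interaction: simulated rejection was .008 to .010. In the baseline-adjusted final-score comparison it does not cancel. With an assumed pre-post correlation of .6, the bias is 0.5 × (1 − .6) = 0.20 SD. Rejection at .008 is then .03, .12 and .29 at m = 25, 75 and 150.

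**7. Can the analysis estimate the cohort component?** Two cohorts minus two condition means leaves 2 − 2 = 0 degrees of freedom. A mixed model or a cluster-robust standard error has nothing to work with.

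**The case against.** The plan has real mitigations. Baseline demographics and wellbeing are prespecified as covariates. The same mentors serve students in both conditions, so mentor effects are crossed with arm. In simulation with ten crossed mentors and a mentor ICC of .05, the error was .005 to .008, which is not inflated. This disposes of mentor clustering as a cause. It does not touch cohort-level change, because the covariates are measured on students and the mentors are common to both cohorts.

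It is also fair to say that the Bonferroni step is offered only as a correction for multiple comparisons, and that the SAP's opening sentence speaks of a relation. But the research question asks about impact, and nothing in the plan stops a significant result being reported as one.

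Several stronger readings are tempting and are not supported:
- A reader might infer that any a.m./p.m. difference can pass as a MentorPRO effect. For the ANOVAs, only differences in pre-to-post change can; stable gaps cancel and matter only for the final-score comparison.
- A reader might infer that students chose mornings or that instructors differed. Neither document says so.
- A reader might take the 150-per-arm figures as expected. The protocol expects fewer students to opt in than the programme holds.
- A reader might take the ICC range as a bound. Nothing in the design caps the ICC.

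Finally, the ICC at which significance is lost is determined by the p-value and m alone. For p = .001 it is about .024 at 25 per arm and .004 at 150. A table of such values therefore adds perspective rather than evidence. That is right, and it makes the table a supplement to the stated limits on inference.

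**Conclusion.** The point holds for differences in change. The planned interaction tests compare two existing class cohorts, and their .008 level is valid for a MentorPRO effect only if cohort-level variance in change is zero. The plan neither states nor defends that condition.

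The size depends on values the documents do not supply. At the arm size suggested by the raffle odds, the error runs from about twice nominal (.017 at an assumed ICC of .01) to about nine times (.075 at .05). The ceiling at full capacity is .371. These figures illustrate the sensitivity; they are not estimates of this trial's error rate. The confounding of cohort with condition depends on none of these assumptions, and the analysis cannot remove it.

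**What to change.** Keep the design and amend the SAP.

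1. Describe the contrast as a non-randomised comparison of two existing class cohorts. State that each p-value assumes no cohort-level difference in change other than through MentorPRO, and that p < .008 alone will not be reported as an effect of MentorPRO. Note that the final-score comparison is also open to bias from stable baseline gaps between the cohorts.
2. As a supporting sensitivity analysis, report for each of the six outcomes the assumed change-score ICC, or the a.m./p.m. drift in SD units, at which significance is lost. Label it as illustrative and not as a bound.

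The cost is SAP wording and one short table. No new data are needed. The price is in the conclusions, which become less favourable to MentorPRO.

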Although preliminary evaluations have shown the promise of the MentorPRO platform for promoting positive student outcomes, additional research is needed with other student populations, especially disadvantaged student populations.

The university in which data was collected for [name] et al. (2023) is a predominately-white institution (43.8% white students, 57.0% white faculty, 59.8% white staff as of Fall 2021) with highly competitive academics (75% of the first year class had a high school GPA above 4.1/5). Therefore, it might be that risk is less pronounced than other universities. Additional research is needed to understand if MentorPRO holds similar efficacy at colleges and universities with more diversity and/or where students are at greater risk of dropping out.

Researching the implementation of MentorPRO in the already-established CLA First, DSP, and SSS programs will allow researchers to measure the impact on student outcomes across more disadvantaged groups that are at higher risk.

Study Population

- The current study will include an evaluation of the MentorPRO app with a program at UMB:
 - The Directions for Student Potential summer program (DSP) invites academically-vulnerable incoming students to participate in a summer preparation course (the summer before their first year). Students are matched with peer mentors who are former DSP students.
- **Inclusion and exclusion criteria:**
 - The inclusion criteria for the current evaluation includes:
 - Being 18 years of age or older
 - Being a current member of DSP
 - Can speak, read, and write in English
 - Has access to a smartphone
 - **Inclusion of vulnerable populations:** All participants will be UMB undergraduate students. Participants will *not* include any prisoners, pregnant women (that we are aware of), anyone under the age of 18, or adults unable to consent.

Study Duration

- All students involved in the DSP summer program will be involved in 6 weeks of academic programming and peer mentoring (June 12th-July 21st), meeting 4 days per week during the summer prior to mentees' first year in college, as well as 3 weeks of post-program peer mentoring (total trial of 9 weeks).

Investigator Protocol

- Investigators will be collecting data between June 2023 and August 2023. After data has been collected, investigators are expected to run analyses, provide reports to partnering programs, and write up manuscripts through summer of 2024.

Number of Participants

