- The DSP Summer program serves up to 300 incoming students.
- At the end of the study, mentors will also be recruited for participation. The estimated number of mentors is 10.
- The number of students who opt into the research activities are expected to be lower than the total number of students in the program.

Setting

- **Sites/locations:**
 - The current study will include an evaluation of the MentorPRO app with DSP.
 - Participants will be involved in an already-established mentoring program through UMB, and will be recruited for additional evaluation efforts from the already-established program.
 - All data collection will occur via online platforms. MentorPRO collects various data points from users directly through the app, including but not limited to: responses to in-app surveys and check-ins, in-app chat messaging, and app engagement. For the students who opt into additional research activities, all surveys will be conducted via UMass Boston's Qualtrics.
- **Prior approvals:** N/A
- **External IRB/ethics review:** N/A
- **Local permissions/local context:** N/A

Recruitment Methods

- **Recruitment process:** During the DSP programming, DSP staff will hand out postcards that has information about the study and a QR code to sign up (Qualtrics). The Qualtrics link will have (in order): an informed consent, an eligibility screener, and if eligible, the pre-intervention survey (Time 1; T1).
 - Students will have time to ask questions, and any questions in which program staff cannot answer will be escalated to the research team. Individuals will also be provided the contact information of the study Principal Investigator ([name]) in the consent form so that they can ask any questions before consenting, if relevant.
- **Recruitment materials:** During the DSP programming, DSP staff will hand out postcards that have information about the study and a QR code to sign up on (Qualtrics). See attached.

Investigator Protocol

- **Screening for eligibility:** All interested participants will be required to take a brief eligibility screening via Qualtrics. If a student does not meet the criteria, the Qualtrics survey will close and not let them proceed with the study. The only inclusion criteria for the current evaluation includes:
 - 18 years of age or older
 - Being a current member of DSP
 - Can speak, read, and write in English
 - Has access to a smartphone
 -

Procedures Involved

- **Study procedures:**
 - **Student mentees:**

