- Students in the **intervention condition** may be recommended a third-party mental health app (Healthy Minds Program; HMP) and be provided supportive accountability (i.e., encouragement, nudges, etc) from their mentor to promote consistent active engagement with HMP. Mentors will have three handouts for HMP; one for how to talk about HMP with students, one for how to provide support to students, and one for students that instructs them on how to download the app. Please see attached handouts (3). Data on students' engagement with HMP will be provided weekly from the Healthy Minds team (exported from Amazon Web Services by the research team) and distributed to the appropriate mentor weekly to inform individual supportive accountability practices.
- All study measures administered via Qualtrics can be found attached. The following data will also be requested from academic records at UMB:
 - Pre-matriculation/High school GPA
 - Course load/credits for fall '23 semester
- Additional data sources:
 - HMI app data
 - Engagement
 - Responses to in-app questionnaires
 - MentorPRO app data
 - Engagement
 - Responses to in-app questionnaires
 - Mentors' engagement in MentorPRO Academy training courses
- Mentors:
 - At the end of the 9 weeks, mentors will be recruited to provide feedback. Interested mentors will fill out an eligibility screener, and, if eligible, an informed consent form, brief demographics survey, and short feedback survey (all through Qualtrics). See the attachment for all mentor measures.
- **Payment/incentives:**
 - Students will receive \$50 for the first survey and \$50 for the final survey. Therefore, if they complete all three surveys, they can earn up to \$100. Payment will be administered to participants via Tango Gift Cards at the end of the study.
 - Mentors will receive \$10 for the feedback survey. Payment will be administered to participants via Tango Gift Cards at the end of the study.

Investigator Protocol

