- o Because students in the **MentorPRO** condition are being asked to do additional tasks (compared to students who are not in the MentorPRO condition), students in the MentorPRO condition will be allowed to participate in a raffle for a MacBook Air (valued at \$899) for the use of MentorPRO. Students in the MentorPRO condition are being asked to use MentorPRO and the Healthy Minds every day, resulting in up to 35 minutes of effort a day. Given this effort, we feel that this opportunity is adequate compensation. If all participants earn a similar number of chances, the probability of winning the MacBook Air is 1/25 (4 % chance).
 - 5 entries for messaging with their Peer Navigator each week through Aug 11
 - Now through July 28
 - July 28-Aug 4
 - Aug 5 - Aug 11
 - 1 entry for each Check-In before Aug 11
 - 5 entries downloading/installing/following directions to get onto Healthy Minds
 - 1 entry for every day of Healthy Minds use after initial use

Students in the MentorPRO condition *who have already consented to the study* will be informed of the raffle via text, email, and/or phone call and will be given the raffle information, including the attached PDFs (explaining the raffle, and how to get started with Healthy Minds). Questions will be answered by research staff.

Data Analysis

- **Data analysis:** The data will be analyzed both quantitatively and qualitatively. The procedures are outlined below to address each of the research questions:
 - o Research Question 1: What is the acceptability and feasibility of the MentorPRO mentoring program?
 - Recruitment, retention, and adherence to the MentorPRO mentoring program and application will be evaluated to determine the acceptability and feasibility of the program.
 - Acceptability of MentorPRO will also be assessed through open-ended questions and surveys commonly used to evaluate online programs.
 - Qualitative analyses will be conducted to evaluate the level of participants' engagement with mentors via the in-app chat messaging feature.
 - Mentors' responses to survey questions will examine initial mentor feasibility and acceptability of MentorPRO.
 - o Research Question 2: Does mentoring with MentorPRO demonstrate an impact on efficacy for student academic outcomes (i.e., GPA) and indices of wellbeing (i.e., mental health, connectedness, academic self-efficacy,

Investigator Protocol

and overall wellbeing) among a diverse sample of incoming or first year college students?

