- Quantitative analyses will be conducted to determine whether level of engagement with mentors and the app (e.g., via frequency of in-app chat messaging, frequency of in-app survey completion and check-ins) relates to changes in academic outcomes and indices of wellbeing, as well as to broadly model how these domains change over the course of students' participation.
- Group comparisons will be conducted to examine if there are differences in final mental health and wellbeing measures across groups (intervention and control). Baseline demographics and wellbeing indices will be used as covariates in analyses.
- Exploratory analyses will also be conducted on the data to examine whether other trends or patterns emerge from the data.
- **Data integrity:**
 - In order to ensure quality control of the data collected via the Qualtrics survey, participants will be prevented from submitting multiple responses by enabling this feature within Qualtrics. Data will be checked for missingness.

Risks to Participants

- The potential risks are minimal for this research project, as a majority of the procedures in this study that participants will be exposed to are no more a risk than what individuals encounter on a daily basis. Participants may experience some emotional discomfort related to assessment questions, which ask about academic performance, emotional wellbeing, and emotional and social functioning. However, asking these questions is pertinent to the goals of this study in order to compare changes on variables throughout the intervention.
- Participants can skip any questions on the survey that they would prefer not to answer or stop participating at any time, which will be made clear on the informed consent and during the survey completion process.
- There is a slight risk for breach of confidentiality as participation in the research is dependent on membership in a UMB program.
- Researchers will have access to identified data from the MentorPRO application and surveys to match data across datasets and for the purpose of compensating individuals for their study participation. All other researchers will receive de-identified matched data. All analyses will be run on de-identified datasets and findings will be reported in aggregate form.
- In the informed consent and debriefing form, there will be information on where to find resources for emotional support at UMB in the rare case that any of the participants need additional support.

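### High school GPA is requested from records but named in no analysis and in no adjustment of the non-randomised a.m./p.m. comparison

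*Protocol*

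**What the plan says.** **Data requested.** Under Procedures Involved, the protocol lists two items from academic records: "Pre-matriculation/High school GPA" and "Course load/credits for fall '23 semester". No college GPA is on that list.

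**Assignment.** The same section allocates by class time: "the a.m. cohort will be assigned to the intervention/MentorPRO condition, while the p.m. cohort receives mentoring as usual". Under Study Population, the program "invites academically-vulnerable incoming students to participate in a summer preparation course".

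**Timing of T1.** Under Recruitment Methods: "During the DSP programming, DSP staff will hand out postcards that has information about the study and a QR code to sign up (Qualtrics". That link leads through consent and screening to the T1 survey.

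**Covariates.** The protocol's Data Analysis section, repeated in the SAP's copy of it, says: "Baseline demographics and wellbeing indices will be used as covariates in analyses".

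**Final model.** The SAP's closing paragraph, which the final report is to follow, says "we will conduct repeated measures ANOVAs with two time points (pre and post summer bridge program". It tests time by condition on three main and three secondary outcomes at .008 each. It states no covariate.

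**GPA elsewhere.** Research Question 2 asks whether MentorPRO can "demonstrate an impact on efficacy for student academic outcomes (i.e., GPA". A separate planned analysis relates engagement to academic change. Neither says what role the high school GPA has.

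**The concern.** With one intact cohort per arm and no randomisation, whatever comparability the analysis can claim has to come from adjustment. These students were invited because of academic vulnerability, and academic self-efficacy and university belonging are among the tested outcomes. Prior attainment is thus a plausible confounder. It also has an advantage over the T1 scores: high school GPA is fixed before the program and does not depend on when, or whether, a student answered a survey item. T1 wellbeing may already reflect some days of the program.

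If the plan is followed as written, this variable is obtained and left out of the group comparison. A cohort difference in attainment that also predicts change would then be read as a MentorPRO effect. If GPA is brought in only after results are seen, the choice is open to the charge of being data-driven.

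**Working it through.** **Textual check.** High school GPA appears once, in the records request. It is not a wellbeing index and would not ordinarily be counted as a demographic, so the covariate sentence does not reach it. The SAP's ANOVAs name no covariate at all, so there GPA shares its absence with the demographics that the covariate sentence promises.

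**The plan's own figure.** 0.05 / 6 = 0.00833, which rounds to the SAP's .008. The documents give no effect size, SD, planned number per arm, GPA gap or GPA correlation, so what follows is an illustration on assumed values.

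**Inputs.**
- α = .008 (SAP).
- n = 25 per arm. The protocol puts the raffle odds for MentorPRO students at 1/25 if chances are similar; an equal control arm is assumed.
- n = 150 per arm as a ceiling only: 300 program places / 2.
- D = cohort gap in GPA, in SDs (assumed).
- r = within-cohort correlation of GPA with change (assumed).
- No true effect.

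**Formulas.** With two time points, the time-by-condition F test equals the two-sample t test on change scores. The bias from omitting GPA, in SDs of change, is D × r. The test statistic then has noncentrality D × r / √(2/n), and the false-positive rate is the two-sided tail of the noncentral t on 2n − 2 degrees of freedom.

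**Worked case.** D = 0.5, r = 0.3, n = 25:
- bias = 0.5 × 0.3 = 0.15 SD;
- standard error = √(2/25) = 0.283;
- noncentrality = 0.15 / 0.283 = 0.53;
- critical t on 48 df = 2.768;
- rejection = 0.0169, or about 1.7% (1.75% if the threshold is left unrounded at .05/6).

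**Range.**

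| D | r | Bias (SD of change) | Rate, 25 per arm | Rate, 150 per arm |
|---|---|---|---|---|
| any | 0 | 0 | 0.8% | 0.8% |
| 0.2 | 0.1 | 0.02 | 0.8% | 0.9% |
| 0.5 | 0.3 | 0.15 | 1.7% | 8.7% |
| 0.5 | 0.5 | 0.25 | 3.6% | 30.9% |

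The bias does not shrink with sample size; a larger sample only makes it easier to declare significant.

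**Effect of adjusting on precision.** Residual variance falls by the factor 1 − r². For r = 0.1 to 0.4 that is a cut of 1% to 16%, equivalent to 1/0.99 = 1.01 to 1/0.84 = 1.19 times the students. Against this, a GPA gap inflates the variance of the adjusted contrast by 1 + D²/4. At D = 0.5 this is 1.0625, so at r = 0.3 the net factor is 0.91 × 1.0625 = 0.967, roughly neutral. At r = 0 and D = 0.5 adjustment would cost about 6% in variance.

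**The case against.** The strongest reply has four parts.

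**GPA may have another use.** A reader might infer that GPA is collected and never used. The documents do not support that. GPA is the named academic outcome of Research Question 2, and high school GPA could be the baseline for the engagement analysis. That use is not spelled out, and no GPA change can be formed from the two listed records alone. In any case, an engagement analysis is not the between-group comparison. What stands is that GPA is named in no analysis and in no between-group adjustment.

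**GPA is not the only pre-program information.** A reader might infer that it is the one baseline measure sure to predate the program. Fixed demographics also predate it whenever they are recorded, and the T1 items are in attachments outside the public documents. GPA is the only pre-program academic measure named.

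**No bias has been shown.** This stands in full. Nothing in the documents shows that the cohorts differ on GPA or that GPA predicts change over nine weeks. A time-by-condition test already removes stable differences in level. Selecting the whole program for academic vulnerability could narrow the range of GPA as easily as it could leave the cohorts different. Nor does it help to note that, at 25 per arm, a gap above 0.3 SD would arise about 29% of the time under random assignment: the nominal error rate already allows for chance imbalance. The case needs systematic sorting by class time. The 150-per-arm figures need every place filled and every student consenting, while the protocol expects fewer to opt in.

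**GPA is a refinement.** The larger gap is that the covariate sentence promises adjustment and the SAP's final model has none. That also stands, and it shapes the fix. GPA may be missing for some students or reported on different school scales, so the cost is more than one degree of freedom.

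**Conclusion.** The point holds as an omission that should be corrected, not as a demonstrated bias. A pre-program academic measure is requested and then left out of every stated adjustment in a comparison that is not randomised.

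At about 25 per arm, the only size the documents imply, the assumed 0.5 SD gap with r = 0.3 roughly doubles the per-test false-positive rate, from 0.8% to about 1.7%. In absolute terms that is modest. The result rests on both assumed values and on equal arms; with r = 0 nothing is lost by omitting GPA. Adjustment would remove only the part of any cohort difference carried by GPA and would not make the a.m. and p.m. cohorts exchangeable. The recommendation is still worth acting on because the variable is already requested and because naming it in advance protects the analysis from a later charge of selection.

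**What to change.** 1. Amend three places consistently: the covariate sentence in the protocol's Data Analysis section, its copy in the SAP, and the SAP's closing paragraph. All six group comparisons should adjust for baseline demographics, baseline wellbeing and pre-matriculation GPA (continuous).
2. Fix the form of the model in advance. Either keep the two-time-point model and enter GPA with its interaction with time (a main effect alone leaves the time-by-condition estimate unadjusted), or use ANCOVA of the T2 score on condition, T1 score, demographics and GPA. ANCOVA fits the covariate sentence more directly, since in the two-time-point model the outcome's own T1 score is already part of the response. The two can give different answers when the cohorts differ at T1, so only one should be primary.
3. Put GPA on a common scale before analysis and state the rule.
4. Keep students without a usable GPA in the analysis, in line with the SAP's intention-to-treat commitment. Imputation is preferable; a missing indicator is simpler but adjusts less completely when the groups are not randomised.
5. Report GPA by cohort in the baseline table, and state what role it has in the academic-outcome and engagement analyses.
6. Do not adjust for fall '23 course load, which can be set after exposure begins.

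**Cost.** A few sentences in two documents, one degree of freedom per model, the work of scaling and imputing GPA, and a small loss of precision if GPA turns out to differ between cohorts but not to predict the outcome. Other a.m./p.m. differences remain and should be stated as a limitation.
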